### **4.2. SAMPLE SIZE AND POWER ESTIMATES**

We used our own institutional data from a previous enteral feeding trial to calculate the sample size for this trial. To detect a 0.5-difference in FFM-for-age Z-scores between groups with SD of 1, 0.05 level of significance, and 80% power for a T-test that compares means from

two independent samples, we estimated that a sample size of 126 patients will be necessary in this superiority trial. Anticipating that approximately 20% of study participants will be lost to follow-up for assessment of the primary outcome at 36 weeks PMA, we will add 12 patients to each group and increase the sample size to 150. We will include a total of 75 patients in each group (n=150).

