### **Risk to Human Subjects**

Human Subjects' Involvement, Characteristics, and Design. In this clinical trial, 150 study participants will be randomly assigned in a 1:1 allocation ratio to receive either a protein-enriched human milk diet (intervention group) or a usual human milk diet (control group) during the first 2 weeks after birth. Patients admitted to the UAB Neonatal Intensive Care Unit between July 2020 and December 2022 will be screened to determine eligibility for the trial. Our study population will reflect the epidemiology of prematurity in the state of Alabama, with approximately 51% being Black (African-American), 47% White (Non-Hispanic Caucasian), and the remaining 2% Hispanic/Other. This study population has been selected based on the frequency of postnatal growth problems observed in extremely preterm infants and the increased risk of adverse health outcomes in this vulnerable population.

Study Procedures, Materials, and Potential Risks. For study participants, data will be collected from electronic medical records. Data containing identifying information will be available only to the PI and research personnel directly involved with this study. Information about the study

will be shared without individual identifiers. Data will be collected from medical records in accordance with the study protocol. This will include demographic data and other nutrition/feeding data. This protocol will be reviewed by the Institutional Review Board of the University of Alabama at Birmingham.

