### **4.1. STATISTICAL ANALYSIS PLAN**

All statistical analyses will use two-tail alpha to reject null hypotheses at 0.05, using R software. Continuous variables will be summarized as means  $\pm$  standard deviations (SD) or as medians and interquartile ranges (IQRs). Categorical variable will be summarized as frequencies and proportions. Group differences will be evaluated using the T Test or Wilcoxon test for continuous variables and chi-square for categorical variables. The effect size of the primary outcome will be expressed as the mean difference with 95% confidence intervals (CIs). Risk ratios (RRs) with 95% CIs will be reported for categorical outcomes. All of the efficacy and safety outcomes of the trial will be analyzed with the intention-to-treat principle.

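### Randomising 150 infants with 20% loss leaves 120 evaluable, not the 126 that Section 4.2 requires, so power is about 77.5% rather than 80%

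*Combined protocol and SAP*

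**What the plan says.** Section 4.2 sets out the calculation in three steps.

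- **Requirement.** The inputs are "To detect a 0.5-difference in FFM-for-age Z-scores between groups with SD of 1, 0.05 level of significance". The target is 80% power, by a two-sample t-test. The result is "we estimated that a sample size of 126 patients will be necessary in this superiority trial". Section 4.1 fixes the sidedness: "All statistical analyses will use two-tail alpha to reject null hypotheses at 0.05, using R software".
- **Expected loss.** "Anticipating that approximately 20% of study participants will be lost to follow-up for assessment of the primary outcome at 36 weeks PMA".
- **Allowance.** "we will add 12 patients to each group and increase the sample size to 150", followed by "We will include a total of 75 patients in each group (n=150").

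The risk part of Section 3.3 repeats the total ("150 study participants will be randomly assigned in a 1:1 allocation ratio"), and the microbiome power statement in Section 4.1 also uses 75 per group. No other section gives a different loss rate or a larger total.

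**The concern.** Section 4.2 expresses the loss as a share of study participants, that is, of the infants randomised. The 24 added infants are close to 20% of the 126 evaluable infants, but they are a smaller share of the 150 randomised. An allowance sized on the evaluable number is always too small when the loss acts on the randomised number.

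This paragraph is the only justification given for the trial's size on the primary efficacy outcome. If the loss occurs as planned, the trial will have fewer evaluable infants than the plan itself calls necessary, and the 80% power will be quoted for a number that the plan does not expect to have.

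**Working it through.** **Inputs** (Sections 4.1 and 4.2): difference 0.5; SD 1; two-sided alpha 0.05; power 80%; two-sample t-test; 1:1 allocation; loss 20% of those randomised; 150 randomised, 75 per group.

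**1. Reproduce the 126.** Normal approximation, per group:

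n = 2(1.96 + 0.8416)² × SD² / difference² = 2 × (2.8016)² / 0.25 = 62.8, so 63 per group and 126 in total.

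This matches the plan. The exact (noncentral t) calculation for the named test gives 63.8, so 64 per group and 128 in total. A one-sided test would need only 50 per group, so the plan's figure is two-sided, as Section 4.1 says.

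**2. Apply the stated loss.**

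- 150 × (1 − 0.20) = 120 evaluable, 60 per group.
- 126 − 120 = 6 infants short.

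**3. Size of the allowance.**

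- 24/126 = 19.0% of the evaluable number.
- 24/150 = 16.0% of the randomised number. This is the largest loss at which 126 remain.

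**4. Total consistent with 20% loss.**

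- From 126: 126/0.8 = 157.5, so 158 (79 per group).
- From the exact 128: 128/0.8 = 160 (80 per group).

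**5. Power at 60 per group.**

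- Normal approximation: 0.5/√(2/60) − 1.96 = 2.739 − 1.960 = 0.779, which gives 78.2%.
- Noncentral t: 77.5%.
- Difference detectable with 80% power (noncentral t): 0.516 Z.

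**6. Power of 150 randomised, by loss rate** (equal loss in both groups):

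| Loss | Evaluable | Power, normal | Power, exact t |
|---|---|---|---|
| 16% | 126 | 80.1% | 79.5% |
| 18% | 123 | 79.2% | 78.5% |
| 20% | 120 | 78.2% | 77.5% |
| 25% (illustrative) | 112.5 | 75.5% | 74.8% |

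**7. Separate the two sources of the gap.** On the exact t scale, the plan's own 63 per group gives 79.5%. The inflation step therefore costs 79.5 − 77.5 = 2.0 points (80.1 − 78.2 = 1.9 on the normal scale). The remaining half point below 80% comes from using the normal formula for a t-test.

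**The case against.** The arithmetic is hard to dispute; the fair objection concerns its importance.

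- **The effect is small.** By the formula that reproduces 126, power falls 1.8 points below 80%. This stands.
- **The gap is within the uncertainty of the inputs.** The SD of 1 and the loss of about 20% are round figures. Since 0.5/0.5157 = 0.97, an SD of 0.97 would restore 80% power with 60 per group, as would baseline covariates explaining about 6% of the variance (1 − 0.97² ≈ 0.06). Section 4.1 plans adjusted analyses that include gestational age and sex. This shows the scale but does not repair the calculation: Section 4.2 is based on an unadjusted t-test, and the documents do not say how much variance the covariates explain.
- **An approximate 20% allows some latitude.** It does, but any loss above 16% leaves fewer than 126, and at 18% power is already 79.2% (normal) or 78.5% (t).
- **The 126 versus 128 difference is minor.** Agreed. The normal approximation is a common planning formula, and 63 per group gives 79.5% by exact t. The point rests on the loss allowance.
- **The cause is inferred.** Multiplying by 1.2 gives 151.2, not 150, and reaches 150 only if 12.6 per group is rounded down to 12. That is a plausible account of the figure, but the plan gives no formula and the conclusion does not depend on one.

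Intention-to-treat analysis does not help either: Section 4.1 gives no method for missing primary outcomes, and Section 4.2 treats these infants as lost.

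**Conclusion.** The concern holds. Under the plan's own effect size, SD, alpha and loss rate, 150 randomised infants yield 120 evaluable. Power is then 77.5% by the named test (78.2% by normal approximation), or 80% for a difference of about 0.52 Z instead of 0.50. The statement is wrong as written, though the shortfall is modest and the trial is not seriously underpowered.

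The result assumes equal loss in the two groups and that the 20% covers every missing primary outcome, including deaths. Section 4.2 does not say whether deaths are counted, although death is a listed safety outcome (Section 3.2.9) in infants of 22 to 26 completed weeks. Counting them within the 20% favours the plan. If they come on top of it, power is lower; the 25% row of the table shows the scale.

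**What to change.** Correct Section 4.2 in one of these ways, and say whether the loss rate includes deaths:

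1. Keep 150 and 20% loss, and state what they deliver: 120 evaluable infants, 77.5% power for a 0.5 Z difference, or 80% power for about 0.52 Z.
2. Keep 150 and the requirement of 126, and state that the design tolerates 16% loss, provided the sponsor's institutional data support that rate.

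Both are rewording only, with no change to enrolment, design or analysis. The cost is a slightly less favourable power statement or a stricter loss assumption.

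If the sponsor prefers to keep both 20% loss and 126 evaluable infants, the total is 158, eight more than planned (160 from the exact t-test figure of 128). The plan's own recruitment figures in Sections 4.3 and 4.4 would accommodate this: 150 eligible per year × 60% consent × 2.5 years = 225.

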#### **4.3. AVAILABLE POPULATION**

The estimated UAB available population based on inclusion/exclusion criteria is 150 per year.

#### **4.4. PROJECTED RECRUITMENT TIME**

Assuming a consent rate of 60%, this trial will require 2.5 years for patient recruitment and 1 year for completion of microbiome analyses. Therefore, the time to study completion is 3.5 years.

#### **4.5. STUDY MONITORING PLAN**

##### **4.5.1. Reporting Adverse Events**

Serious adverse events and suspected unexpected serious adverse reactions will be reported to the Data Safety and Monitoring Board (DSMB).

##### **4.5.2. Data Monitoring Plan and Stopping Rules**

Because not all neonatal units across the United States increase protein intake during the first 2 weeks after birth in extremely preterm infants, our DSMB will analyze all serious adverse events during the trial to determine whether they were result or consequence of participation in the trial. Unless modification or cessation of the protocol is recommended by the DSMB, the trial investigators will be unaware of the preliminary results described in these reports. Any provider or caregiver involved in the trial will be able to write to the DSMB to draw attention to any concern they may have about the possibility of harm arising from the intervention under investigation. The attending clinician may also withdraw the infant from the study if they consider this to be in the best interest of the infant's health and well-being.

